## **12.0 CRITERIA FOR THERAPEUTIC RESPONSE/OUTCOME ASSESSMENT**

All patients will undergo contrast enhanced triple phase CT within 6 weeks of registration and then again within 2-3 weeks of completing their first treatment. Prior to treatment index lesions according to RECIST will be identified and conventional uni-dimensional measurements obtained blinded to the patients treatment group assignment. Response to treatment will be assessed by conventional RECIST criteria (see **Section 4.1**). The electronic data will then be sent to an independent imaging laboratory where an imager not familiar with the same patient's initial data set will create a volumetric profile including volume of tumor and volume of necrosis at time 0. On the initial post-treatment scans the index tumor(s) will once again be identified and measured by an imager blinded to the patient's treatment group, and once again the electronic data will be sent to the imaging laboratory where it will be independently analyzed volumetrically, once again recording tumor volume, and volume of necrosis. These results will be recorded in the electronic database. These linear and volumetric assessments will be repeated each time the patient is imaged for the duration of the study. Any increase in standard manual measurements of >20%, or the development of > 75% increase in enhancing tumor volume will be considered evidence of progression of disease (PD) and so recorded. In addition, patients who develop  $\leq 5\%$  necrosis, by volume, following the initial treatment, or increase of >50% in sum of uni-dimensional measurements following subsequent treatments will be considered treatment failures.

### **Volumetric Imaging Method**

We have developed a system with a practical user interface that allows operator to synchronically view baseline and corresponding follow-up images of the liver side-by-side, semi automatically delineate tumor contours, and segment necrosis with an optimal threshold determined by observing segmentation results while varying thresholds or setting a system wide threshold value. If a segmentation result is suboptimal, the system allows the operator to make manual correction (Fig 2).

[figure not shown]
**Figure 2** An image processing system allows manual segmentation of liver tumor (with blue border) and tumor necrosis (area in red). Segmented tumor contours and necrosis areas are superimposed on baseline (left) and follow-up (right) CT images. Tumor volume increased 29.5%, whereas ratio of tumor necrosis volume to tumor volume increased 388.8%.

Segmented tumor contours and necrosis areas are superimposed on baseline (left) and follow-up (right) CT images. Tumor volume increased 29.5%, whereas ratio of necrosis volume to tumor volume increased 388.8%.

In addition to the manual segmentation and semi-automated segmentation, we plan to develop a fully automated segmentation algorithm for separating tumor from normal hepatic parenchyma as well as necrosis from tumor. These are extremely difficult segmentation tasks, because 1) the intensity contrast between tumor and liver parenchyma can be very low, and 2) necrosis can be heterogeneous throughout the tumor and may be difficult to be distinguished from hypointense portions of the tumor.

### Automated/Semi-Automated Segmentation of Tumor

Previously, we developed a computer algorithm for semi-automated delineation of liver metastases from colorectal cancer. The algorithm starts with a manual selection of a seed lesion region-of-interest (ROI). Based on intensity distributions of the seed ROI and the liver parenchyma, several features were computed and used to adaptively guide the region-growing. To prevent the region-growing from leaking into surrounding tissues of similar characteristics, specific shape constraints, including a local shape, a global shape and a gravity-shift index, were developed to jointly control the iteration of the region-growing. [Zhao B 2006] Figure 3 shows two examples of the segmentation results obtained using the algorithm.

**Figure 3** Semi-automated segmentation of liver metastasis using a shape-constrained region-growing algorithm.

In this study, due to similarity of the tumor appearance, we will adopt the same segmentation strategy. However, some portions of the algorithm may need to be modified and some of the intensity-based features may need to be redefined, especially their threshold values. For instance, the lower threshold of the intensity sub-range IV used in the previous algorithm may need to be increased because of possible bright parts of tumor in this study.

#### **Automated/Semi-Automated Segmentation of Necrosis**

Once a tumor is delineated, necrosis inside the tumor needs to be detected and segmented. As necrosis will not be enhanced by the contrast material, it appears low attenuation and possesses a certain low range of intensity on contrast-enhanced CT images. We determine this intensity range through manually extracting necroses in a large number of liver tumors and calculating the mean and standard deviation (std) of the necroses' intensity. A fixed threshold can then be determined by the equation:  $Thr = \text{mean} + a * \text{std}$ , where  $a$  is a parameter that needs to be optimized in the study. Any voxel in the tumor having an intensity value lower than  $Thr$  will be considered as a necrosis voxel. This value may be modified on a scan or patient basis and will be visually validated by the Radiologist. Volumetric tumor size and necrosis can therefore be calculated simply for an entire tumor or series of tumors.

#### **Tumor Response**

Tumor response will be measured according to RECIST criteria, as well as using the new volumetric method of assessing non-viable tumor. In the case of differences between these criteria, the RECIST criteria will be used for clinical judgment and decisions.

RECIST criteria responses are defined as follows:

Complete Response (CR):	disappearance of all target lesions (up to 10 target lesions) confirmed at $\geq 4$ weeks
Partial Response (PR):	$\geq 30\%$ decrease from baseline
Stable Disease (SD):	All other cases
Progressive Disease (PD):	$\geq 20\%$ increase from the smallest sum of measurements since the start of treatment
Objective Response:	CR and PR

#### **Measurement of Treatment Response**

Contrast enhanced CT and MRI are the best currently available methods of evaluating response to treatment for HCC, and the most reproducible means of measuring target lesions and assessing

necrosis. Triple phase contrast enhanced scans will be performed in accordance with protocol detailed in “Follow-up after complete treatment” section.

### **Verification of Tumor Response**

Tumor response assessments will be recorded in CRF by the investigator. Triple phase CT scans will be read from PACS workstation by independent readers without knowledge of the treatment group or investigator opinion.

### **Local Tumor Response**

Local tumor response will be determined for the initial tumor volume treated following each complete treatment and be recorded as CR, PR, SD, or PD by RECIST and volumetric methods. New tumor developing in a distant previously untreated area of the liver will be considered new hepatic progression (NHP)

## **13.0 CRITERIA FOR REMOVAL FROM STUDY**

If the patient develops < 5% necrosis by volume following the initial treatment, or increase of >50% in sum of uni-dimensional measurements following subsequent treatments he/she will be considered a treatment failure and will be taken off study and referred for alternative therapy.

If at any time the patient develops unacceptable toxicity he/she will be removed from study.

Known or suspected pregnancy will result in withdrawal of patient from study.

If at anytime the patient is found to be ineligible for the protocol as designated in the section on Criteria for Patient/Subject Eligibility (i.e., a change in diagnosis or condition), including an LVEF of <50%, the patient will be removed from the study.

Non-compliance, patient preference.

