## 1.0 PROTOCOL SUMMARY AND/OR SCHEMA

Purpose:	The objective of this study is to evaluate hepatic arterial embolization for hepatocellular cancer using microscopic beads and the same microscopic beads loaded with doxorubicin.
Study design:	Single center, single blind, prospective, randomized phase II controlled, to be conducted without crossover with patients recruited over a 2 year period
Study agents:	Biocompatibles LC Bead ( Beads + doxorubicin ), 100-300 microns, 150 mg doxorubicin per procedure with additional 100-300 micron and larger size beads (Bead Block) as necessary to achieve stasis  Bead Block ( Beads ) microsphere, 100-300 micron with additional larger size beads as necessary to achieve stasis
Limitations of Study	LC Bead and Bead Block are both tinted blue. Because doxorubicin is red, the addition of doxorubicin to the embolization microspheres will change the color of the spheres to some degree, and thus it may be possible for the interventional radiologist performing the embolization to differentiate between the two embolics. All other participants performing image and data analysis will be blinded.
Enrollment:	100 patients will be enrolled, 50 in each study arm
Clinical site:	Memorial Sloan-Kettering Cancer Center, NY, NY
Primary endpoint:	Response to treatment by RECIST criteria
Secondary endpoints:	

• Tumor necrosis

• Toxicity

• Time to progression

• Survival

Safety endpoint:	The safety endpoint will be treatment related Serious Adverse Event (SAE) rate, defined by SAE occurring within 30 days of a procedure. SAE is defined as a grade 3 or 4 adverse event using the Common Terminology Criteria for Adverse Events (CTCAE) 3.0.
Primary analysis:	Intent-to-treat analysis
Secondary Analysis:	Per protocol analysis and treated population analysis
Principle Investigator:	[name]

Member  
Department of Radiology  
Memorial Sloan-Kettering Cancer Center  
[name]  
[name]

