### **Time to Treatment Failure**

Time to treatment failure (TTF) will be measured as the time from randomization until treatment discontinuation for any reason including, development of  $\leq 5\%$  necrosis, by volume, following the initial treatment or  $>50\%$  increase in sum of uni-dimensional measurements following later treatments, treatment toxicity, patient preference, or death.

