### **Time 0 + 11-12 months**

Patients will be seen in clinic and have vital signs (weight, blood pressure, temperature, heart rate), CBC, chemistry profile with liver function tests, coagulation studies, and AFP, and ECOG assessment. They will have a triple phase CT scan. Patients with stable disease compared to the previous scan will be followed up in 3 months. If there is evidence of recurrent or new tumor a repeat treatment will be scheduled within their original treatment arm within 6 weeks of the follow-up scan. The patients will be re-treated with same embolic agent used for first treatment, with embolization protocol identical to that outlined above. They will then re-enter the follow-up pathway. Within one year patients will not receive more than 3 embolizations with LC Bead in order to ensure that they are not exposed to >450 mg of doxorubicin/annum.

Patients who remain disease free (CR), or who have stable disease (SD) at this point, will have follow-up triple phase CT every 3-6 months until death or progression and will only be re-treated for progression or new tumor.

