#### Data Needing to be Entered:

- The date the adverse event occurred
- The adverse event
- Relationship of the adverse event to the treatment (drug, device, or intervention)
- If the AE was expected
- The severity of the AE
- The intervention
- Detailed text that includes the following information:
  - A explanation of how the AE was handled
  - A description of the subject's condition

- Indication if the subject remains on the study
- If an amendment will need to be made to the protocol and/or consent form

The PI's signature and the date it was signed are required on the completed report.

For IND/IDE protocols:

Only UADEs and patient deaths will be reported to the FDA as they occur. For these reports, The CRDB AE report should be completed as above and the FDA assigned IND/IDE number written at the top of the report. If appropriate, the report will be forwarded to the FDA by the SAE staff through the IND Office. **All other SAEs will be recorded as part of the study's data and will be included in the study's progress reports to the FDA.**

This study will collect all SAEs that occur from date of consent until the patient is off study. Since elevation in liver function tests is expected in the immediate post treatment period, no elevation in liver function tests occurring within 2 weeks following treatment will be reported as an SAE, although all elevations will be recorded and captured among the data for the study. The following is a list of the liver function tests: Alkaline Phosphatase, ALT, AST, and Bilirubin. All other elevations to Grade 3 or 4, along with any hospitalization will be reported as SAEs and only reported to the FDA as they occur if considered an UADE.

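### Section 13 takes patients off study, not only off treatment, which cuts SAE collection short and leaves progression and survival follow-up after removal undefined

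*Combined protocol and SAP*

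**What the plan says.** Section 13.0 lists the grounds for removal. For less than 5% necrosis after the initial treatment, or more than 50% growth after later ones, "he/she will be considered a treatment failure and will be taken off study and referred for alternative therapy". For toxicity: "If at any time the patient develops unacceptable toxicity he/she will be removed from study". For loss of eligibility, "including an LVEF of <50%, the patient will be removed from the study".

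The LVEF rule acts in one arm. Section 6.2 limits the exclusion to patients randomised to LC Bead. Section 8.0 and footnote 1 of the Section 10.0 table schedule the echo or MUGA scan for that arm only, with assignment already known.

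Section 4.1 (Time to Treatment Failure) uses the same necrosis, growth and toxicity grounds but treats them as the end of treatment: "time from randomization until treatment discontinuation for any reason including".

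On safety, Section 17.2 states: "This study will collect all SAEs that occur from date of consent until the patient is off study". The safety endpoint in Section 1.0 is the treatment-related SAE rate, "defined by SAE occurring within 30 days of a procedure".

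On follow-up, patients who are re-treated go back into the follow-up pathway (Section 10.0, footnote 7 and the visits from 10-14 weeks on). After 11-12 months, patients in complete response or with stable disease "will have follow-up triple phase CT every 3-6 months until death or progression". Section 14.0 plans Kaplan-Meier and log-rank analyses of TTP and survival and assumes a median follow-up of 3 years. It calls these outcomes censored but gives no censoring rule. The primary analysis is named as "Intent-to-treat analysis".

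**The concern.** Stopping an assigned treatment and ceasing to observe a patient are different events, and the documents use one set of criteria for both. Section 17.2 gives the off-study status a direct consequence for data, so the distinction is more than terminology.

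The grounds for removal are unlikely to be independent of outcome. Little necrosis, rapid growth, toxicity and a falling ejection fraction may all mark a worse course. Kaplan-Meier estimation assumes that patients censored at a given time have the same future risk as those still observed. If removal ends observation, that assumption is doubtful for survival, and the LVEF ground can operate in one arm only.

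One stated aim is hit directly. Sections 2.0 and 14.0 relate necrosis to TTP and survival. The necrosis rule would end follow-up in exactly the patients with the least necrosis, so the low end of that relationship would hardly be observed.

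**Working it through.** The plan states no figure for removal, so most of the check sets the rules side by side. The arithmetic is day counts plus one labelled illustration.

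**1. Which outcome each ground exposes, if observation ends at removal**

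| Ground | 30-day SAE window | TTP | Survival | Primary response |
|---|---|---|---|---|
| Low necrosis | only if decided before day 30 | exposed | exposed | already read |
| Growth above 50% | if within 30 days of a procedure | local event should already be recorded | exposed | already read |
| Toxicity | if within 30 days | exposed | exposed | missing if before the response CT |
| LVEF below 50% | none if found before any procedure | exposed, one arm | exposed, one arm | missing if before the response CT |

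Growth: Sections 4.1 and 12.0 record progression at a 20% increase and set failure at more than 50%, so a patient removed for growth has normally had a local TTP event. Distant and extra-hepatic progression, and survival, remain open.

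Primary response: it is read on the CT 2-3 weeks after Time 0, and Time 0 is the completed treatment (Section 10.0, footnote 3). With a second session 2-6 weeks after the first, that CT can fall 6 + 3 = 9 weeks after the first embolization. There is therefore time for a toxicity removal before it, and a baseline LVEF failure also precedes it.

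**2. SAE window**

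Days lost = 30 - d for removal on day d after the last procedure.
- Necrosis rule acted on at the 2-3 week CT: 30 - 14 = 16 days to 30 - 21 = 9 days.
- Necrosis rule acted on at the 10-14 week CT: 0 days.

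One patient in an arm of 50 is 1/50 = 2.0 points on an SAE rate or a response rate. For scale, the plan's ±14% precision reproduces as 1.96 × √(0.5 × 0.5 / 50) = 0.139.

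**3. Survival level: illustration only**

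Inputs: 2-year survival 68%, from the institutional series in Section 3.0. Assumed: fraction removed f = 5%, 10% or 20%; removed patients have twice the hazard (m = 2); removal at c = 2.5 weeks (0.048 years) or 12 weeks (0.231 years); no contact after removal.

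The hazard h of the other patients solves (1 - f)·exp(-2h) + f·exp(-2hm) = 0.68. If removed patients are censored at c, the Kaplan-Meier estimate at 2 years tends to [(1 - f)·exp(-hc) + f·exp(-hmc)] × exp(-h(2 - c)).

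| f | h per year | KM, removal at 2.5 weeks | excess over 68% | KM, removal at 12 weeks | excess over 68% |
|---|---|---|---|---|---|
| 5% | 0.185 | 69.0% | 1.0 | 68.9% | 0.9 |
| 10% | 0.178 | 70.0% | 2.0 | 69.8% | 1.8 |
| 20% | 0.164 | 71.9% | 3.9 | 71.5% | 3.5 |

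Worked line for f = 10%, 2.5 weeks: 0.9907 × 0.7070 = 0.700. With m = 1 the excess is zero.

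Limit of the model: carried to 3 years it gives about 56% survival, against 42% in the same Section 3.0 series. I therefore use it at 2 years only and draw no 3-year death counts or hazard ratios from it.

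**The case against.** The strongest reply is that off study may simply have meant off treatment. Section 13.0 never says that data collection stops, Section 4.1 uses the same grounds for treatment discontinuation, and a 3-year median follow-up makes little sense if removed patients are lost. Vital status may well be collected. That is a fair reading, and it is why the bias is stated conditionally. It does not remove the point: no section says so, and Section 17.2 ties SAE collection to off-study status in plain terms.

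Second, the SAE gap is narrow. A patient removed for toxicity will usually already count as having an event, and a baseline LVEF failure has had no procedure. This stands. What remains is a window that the stated rules do not complete for every treated patient.

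Third, Section 14.0 describes the study as one of estimation and the survival aim as preliminary. This also stands and limits the weight of the point, although those survival data are meant to plan a later trial.

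Some stronger readings are tempting but unsupported. A reader might infer that follow-up ends for everyone who progresses. It does not, because patients below the failure threshold are re-treated and re-enter follow-up. A reader might infer that removed patients leave the ITT set. Section 13.0 does not say that. The opposite inference, that ITT fully protects the primary endpoint, also fails: it keeps the denominator but does not supply a response that was never measured.

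**Conclusion.** The point holds, mainly for the safety and secondary analyses. The documents do not separate stopping treatment from ending follow-up. SAE collection ends at removal although the endpoint needs 30 days, and follow-up after removal and TTP censoring are undefined. The primary response is touched only where a patient is removed for LVEF or toxicity before the response CT.

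The size cannot be computed, because no removal rates or prognostic effects are given. The 1 to 4 point overstatement of 2-year survival rests on assumed removal of 5-20%, a doubled hazard and complete loss of contact. A reader might infer that the comparison between arms is materially biased. The documents do not support that: it would need removal, or the prognosis of removed patients, to differ between arms, and equal removal of similar patients would cause no shift. The one-arm LVEF rule makes a difference possible but does not establish its size.

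This should be fixed, because the change is cheap and data not collected cannot be recovered at analysis.

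**What to change.** Leave the criteria for stopping treatment unchanged.

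- **Section 13.0.** For the necrosis, growth, toxicity and ineligibility (LVEF) rules, replace removal from the study with: *stops study treatment, remains in the ITT set in the assigned arm, and is followed for SAEs through 30 days after the last procedure, for progression on available CTs, and for survival to the analysis cut-off*.
- **Section 17.2.** Run SAE collection to the later of off study and 30 days after the last procedure.
- **Section 14.0, primary response.** State that randomised patients with no response CT, including LVEF exclusions found after randomisation, stay in the ITT denominator as non-responders.
- **Section 14.0, TTP.** State that TTP is not censored at removal, and that patients with no progression seen are censored at the last evaluable CT. Add a sensitivity analysis that counts removal before progression as a TTP event.
- **Time to treatment failure (TTF).** Report it separately, not as that sensitivity analysis. A patient with 20-50% growth has a TTP event but need not have a TTF event, while death and patient preference are TTF events.
- **Reconcile.** The necrosis cut-off is below 5% in the Protocol Schema and Section 13.0, but 5% or less in Sections 4.1 and 12.0. The CT that triggers the necrosis decision also needs one statement: the Schema and the 10-14 week visit place the choice between failure and re-treatment at that later scan, while Sections 12.0 and 13.0 name none. The sponsor should settle both.

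Cost: amendment wording, vital-status follow-up, and SAE collection to day 30 for patients who stop early. No new procedure is needed. The drawback is that TTP after removal will partly reflect later therapy, which is why the sensitivity analysis is included.

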### Protocol Schema

TPCT = Pre-treatment triple-phase CT

TPCT = CT to be used to determine response to treatment (first study endpoint)

TPCT - If there is evidence of persistent or progressive tumor on this follow-up CT (but not meeting criteria for treatment failure), patients are re-treated within their treatment arm, and then re-enter F/U pathway. Treatment failure = < 5% necrosis following the initial treatment, or development of >50% increase in uni-dimensional measurement (RECIST) following subsequent treatments.

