### **Secondary Objectives**

1. Quantify the amount of tumor necrosis before and after initial treatment in both groups by CT volumetry, and correlate with response to treatment by RECIST criteria.
2. Evaluate toxicity, time to progression (TTP) and survival in each treatment arm.  
Determine if initial imaging response to treatment, as manifested by either RECIST criteria or volume of necrosis correlates with either TTP (by RECIST or volumetric method) or survival.

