### **Time to Progression**

Time to progression (TTP) will include and be categorized as time to: local tumor progression (LTP), distant hepatic progression (DHP), and extra-hepatic progression (EHP). Local tumor progression (LTP) will be measured as the time from randomization until the first measurement of progression as determined by the central reading group using RECIST criteria as well as volumetric criteria for the target tumor. Local tumor progression (LTP) will be defined specifically as  $\geq 20\%$  increase from the smallest sum of measurements since the start of treatment (RECIST criteria, see above), or  $\geq 75\%$  increase in enhancing tumor volume. Distant hepatic progression (DHP) will be defined as the development of any new discontinuous disease within the liver, and the development of any extra-hepatic disease will constitute extra-hepatic progression (EHP).

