## **Time 0 + 10-14 weeks**

Patients will be seen in clinic and have vital signs evaluation (weight, blood pressure, temperature, and heart rate), CBC, chemistry profile with liver function tests, coagulation studies, AFP level, and ECOG assessment. They will have a triple phase CT scan. This CT scan will be used to determine if the patients need re-treatment. Patients with evidence of persistent or progressive tumor but who do not meet the criteria for treatment failure, will be re-treated within their original treatment arm within 6 weeks of this follow-up scan. The patients will be re-treated with same embolic agent used for first treatment, with embolization protocol identical to that outlined above. They will then re-enter the follow-up pathway.

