Another secondary objective is to establish whether the use of the doxorubicin eluting beads might prolong time to progression (TTP), or survival, and if initial imaging response to treatment, as manifested by necrosis, correlates with either endpoint. This aim relates to analysis with censored outcomes (time-to-progression and survival time). We will use the Kaplan-Meier method to estimate the survival probabilities and we will use the log-rank test to compare groups. With 50 patients in each arm, we will have approximately 80% power to detect a hazard ratio of 3, assuming a median follow-up of 3 years (i.e., about half of the patients expiring) and controlling the Type I error rate at 5%. A hazard ratio of 3 corresponds to improving the median survival by three-fold or improving two-year survival by approximately 20%. We do not anticipate a survival difference of this magnitude so this aim will primarily serve to obtain preliminary data to plan a future definitive trial.

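### Treatment failures are removed from the study rather than from study treatment, with no written survival follow-up, so survival and some TTP data may be censored for reasons tied to prognosis

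*Combined protocol and SAP*

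**What the plan says.** Section 13.0 defines treatment failure by two triggers: necrosis below 5% by volume after the initial treatment, or growth of more than 50% in the sum of uni-dimensional measurements after subsequent treatments. In either case, "he/she will be considered a treatment failure and will be taken off study and referred for alternative therapy". Section 17.2 ends the collection of serious adverse events when the patient leaves the study.

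Section 10.0 limits re-treatment to non-failures: "Patients with evidence of persistent or progressive tumor but who do not meet the criteria for treatment failure, will be re-treated". The only wording in section 10.0 that carries follow-up to death is for patients in complete response or with stable disease at 11-12 months, who "will have follow-up triple phase CT every 3-6 months until death or progression".

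Section 4.1 counts low necrosis as an event for one endpoint: "Time to treatment failure (TTF) will be measured as the time from randomization until treatment discontinuation for any reason", with low necrosis among the listed reasons. TTP, in the same section, is built from local, distant hepatic and extra-hepatic progression, and low necrosis is not among its events.

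For analysis, section 1.0 names intent-to-treat as primary. Section 14.0 states: "We will use the Kaplan-Meier method to estimate the survival probabilities and we will use the log-rank test to compare groups". It assumes a median follow-up of three years with about half of the patients dying. It gives no censoring rule and does not mention follow-up after removal. Section 2.0 adds a further aim: "Determine if initial imaging response to treatment, as manifested by either RECIST criteria or volume of necrosis correlates with either TTP" or survival.

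**The concern.** Kaplan-Meier and log-rank treat a censored patient as having the same outlook as those still followed. A patient censored because the tumour barely necrosed, or because it grew by more than half, may well have a worse outlook. Whether necrosis predicts outcome is one of the questions the study asks.

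The two triggers act differently.

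- **Low necrosis.** Patients could leave at or soon after the 2-3 week CT. Because low necrosis is not a TTP event, both survival and TTP would be censored in those who have not yet progressed.
- **Growth over 50%.** An increase of this size also meets the 20% progression rule, so the TTP event has been recorded. Only survival afterwards would be lost.

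At stake are the survival estimate in each arm and the between-arm comparison. Section 3.0 says a TTP or survival gain, coupled with a response difference, might serve as the basis for a phase III trial. Section 14.0 wants the survival aim to supply data for planning one. If doxorubicin works by raising necrosis, the control arm would lose more poor-prognosis patients, and the arms would look more alike than they are.

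**Working it through.** **The plan's own figures.** The primary precision reproduces: 1.96 × √(0.25/50) = 13.9%, stated as 14%. The survival power of about 80% for a hazard ratio of 3 does not reproduce with 50 deaths: Φ(½ × √50 × ln 3 − 1.96) = Φ(1.92) = 97.3% (Schoenfeld, two-sided 5%). This point does not rest on that figure. If 10% of the deaths were lost, 45 deaths would still give 95.8%. Lost power is therefore minor, and the issue is bias.

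**Inputs for the low-necrosis trigger.** The documents give no removal share and no prognosis for those removed, so both are assumptions.
- Patients who stay: 85% and 68% survival at one and two years (the centre's own series, section 3.0 Preliminary Data).
- Patients removed, poor case: 56% and 31%, borrowed from another treated series in the same section.
- Patients removed, milder case: the geometric midpoint, √(0.85 × 0.56) = 69% and √(0.68 × 0.31) = 46%.
- Share removed, s: 2%, 5%, 10% or 15%.
- Censoring time, c: week 3 (the response CT) or week 12 (the CT that decides re-treatment), with constant hazard in year one.

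**Formulas.**
- True two-year survival = (1 − s) × 0.68 + s × S_rem(2).
- Kaplan-Meier limit = [(1 − s) × S_stay(c) + s × S_rem(c)] × 0.68 / S_stay(c).
- Standard error per arm = √(p(1 − p)/50), with p the true value.

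**One case in full (poor prognosis, s = 5%, week 3).** S_stay(3/52) = 0.85^(3/52) = 0.9907 and S_rem(3/52) = 0.56^(3/52) = 0.9671. True = 0.95 × 0.68 + 0.05 × 0.31 = 66.15%. Kaplan-Meier = (0.95 × 0.9907 + 0.05 × 0.9671) × 0.68 / 0.9907 = 67.92%. Bias = 1.77 points, against a standard error of 6.69.

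| Share removed | True, poor case | Bias, poor case (week 12 to week 3) | In standard errors | Bias, milder case |
|---|---|---|---|---|
| 2% | 67.26% | 0.6-0.7 | 0.1 | 0.4 |
| 5% | 66.15% | 1.5-1.8 | 0.2-0.3 | 0.9-1.1 |
| 10% | 64.30% | 3.1-3.5 | 0.5 | 1.9-2.1 |
| 15% | 62.45% | 4.6-5.3 | 0.7-0.8 | 2.8-3.2 |

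In the poor case the bias reaches one standard error at about 20% removed (week 3) or 23% (week 12). If necrosis is not prognostic, it is zero.

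**Arm difference (poor case).** Take 15% removed in one arm and 5% in the other. The true difference is 66.15 − 62.45 = 3.7 points. Kaplan-Meier shows 0.2 (week 3) or 0.6 (week 12). The standard error of the difference is √(0.6245 × 0.3755/50 + 0.6615 × 0.3385/50) = 9.6 points.

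**Growth trigger, survival only.** Assume a constant death hazard λ before the trigger, k times λ after it, and a constant trigger hazard. Solve for the two hazards so that true two-year survival is 68% and a share p reaches the trigger by two years. Kaplan-Meier with the trigger censored tends to exp(−2λ), so the bias is exp(−2λ) − 0.68:

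| k | p = 10% | p = 20% | p = 30% |
|---|---|---|---|
| 1.5 | 0.7 | 1.5 | 2.2 |
| 2 | 1.4 | 2.7 | 4.0 |
| 3 | 2.4 | 4.6 | 6.6 |

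The standard error at 68% is √(0.68 × 0.32/50) = 6.6 points, so only the extreme corner of this table reaches it. Both k and p are assumptions.

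**The case against.** The best reply is that the loss of data is inferred. No sentence says vital status stops, and no censoring rule is stated. The protocol describes no survival follow-up procedure for any patient, so silence about failures may only mean that deaths are collected outside the CT schedule. Intent-to-treat and a three-year median follow-up fit that reading better than stopping at week 3. This stands as a limit on certainty. It does not remove the problem, because section 13.0 is a stated rule, its wording is removal from the study, and section 17.2 treats that point as the end of safety data collection.

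A reader might infer that section 10.0 shuts failures out of the visits and scans. It does not. The failure exclusion there and in the Protocol Schema governs re-treatment, while the clinic visits and CTs are written for patients generally. Some failures may therefore have the 10-14 week scan, which is why the working gives both week 3 and week 12.

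A reader might also infer that all of the censoring depends on necrosis, or that the necrosis-outcome relation itself is biased. Only the first trigger depends on necrosis. Where censoring depends only on necrosis, an analysis that conditions on necrosis mainly loses precision at the low end.

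The reply is also right that the magnitudes rest on assumptions. Section 3.0 cites a 78% objective response by EASL criteria at six months with doxorubicin beads. That makes under 5% necrosis in 20% or more of that arm look unlikely, though it is a different trial and criterion. A 3.7-point difference could not be detected with 50 per arm even with complete follow-up.

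**Conclusion.** The point holds in a limited form. Applied as written, section 13.0 would end follow-up for reasons related to prognosis: necrosis for the first trigger (survival, and TTP in those not yet progressed) and growth for the second (survival only). The direction, if these patients do worse, is overstated Kaplan-Meier survival and a smaller apparent arm difference where the effect acts through necrosis.

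The size is not known. For the low-necrosis trigger it is about 0.4 to 5 points of two-year survival for 2-15% removed, below one standard error. This rests on the assumed removal share, prognosis and censoring time.

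The documents do not support reading this as a threat to the trial's main result. The primary response rate is read from the same 2-3 week CT that shows the necrosis, so removal afterwards does not touch it. Section 14.0 says the study is not meant to test a hypothesis and calls the survival aim preliminary. The change should be made because it is cheap and because uncollected deaths may be hard to recover later.

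**What to change.** - **Section 13.0:** for treatment failures, provide for removal from study treatment instead of removal from the study.
- **Section 14.0:** state that all randomised patients are followed for survival until death or end of study under intent-to-treat, and that therapy after failure is recorded.
- **TTP:** add a sensitivity analysis that counts removal for treatment failure as an event. This limits the TTP problem but does not fully remove it, since later progression may go unseen or be altered by other therapy. The analysis will also overlap with the time-to-treatment-failure endpoint already defined in section 4.1.

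The cost is a few words in section 13.0, short additions to section 14.0, and a small amount of vital-status follow-up. No additional protocol CT is proposed. Later survival in these patients may partly reflect the alternative therapy, which is why it should be recorded.
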